13.3.2 Prior Anti-Cancer Therapies

The prior anti-cancer therapies are collected under the “Prior Anti-Cancer Drug Therapies Details”, “Prior Anti-Cancer Radiotherapy Details” and “Prior Anti-Cancer Surgeries Details” eCRF pages.

The number of subjects in each of the following anti-cancer therapy categories will be tabulated:

- Subjects with at least one type of prior anti-cancer treatment
- Subjects with at least one prior anti-cancer drug therapy for metastatic disease
- Subjects with at least one prior anti-cancer radiotherapy
- Subjects with at least one prior anti-cancer surgery

Prior anti-cancer drug therapy will be summarized as follows:

- Number of subjects with at least one prior anti-cancer drug therapy for metastatic disease
- Number of any prior anti-cancer therapy regimens for metastatic disease: missing / 1 / 2 / 3 / ≥ 4
- Number of prior anti-cancer therapy lines for locally advanced disease only: missing / 1 / 2 / 3 / ≥ 4 . If the disease setting is locally advanced, it will be counted into therapy lines for locally advanced disease.
- Number of prior anti-cancer therapy lines for metastatic disease only: missing / 1 / 2 / 3 / ≥ 4 . If the disease setting is metastatic, it will be counted into therapy lines for metastatic disease.
- Type of prior anti-cancer therapy: Chemotherapy for metastatic disease / Chemotherapy for non-metastatic disease / Hormonal therapy / Antibody therapy / Kinase inhibitors / Vaccines / Other
- Disease setting: Neo-Adjuvant / Adjuvant / Metastatic / Locally advanced
- Best response: Complete Response (CR) / Partial Response (PR) / Stable Disease (SD) / Progressive Disease (PD) / Not assessable / Unknown / Not applicable. Best response is derived from the last treatment regimen

The prior anti-cancer drugs will also be extensively detailed with the number and percentage of subjects by the drug class and PT in a table. A subject will be counted only once within a given drug class and within a given drug name, even if he/she received the same medication at different times. The summary will be sorted on decreasing frequency of drug class and decreasing frequency of drug name in a given drug class. In case of equal frequency regarding drug class (respectively drug name), alphabetical order will be used.

The listings of prior anti-cancer treatments and procedures will also be provided: a) listing of prior anti-cancer drug therapies for non-metastatic and for metastatic disease, b) listing of prior anti-cancer radiotherapy and c) listing of prior anti-cancer surgeries. These will include the subject identification number, and all the relevant collected data-fields on the corresponding eCRF pages.

14 Previous or Concomitant Medications/Procedures

Analysis sets: ITT analysis set / Safety analysis set

14.1 Prior and Concomitant Medications/Procedures

Concomitant medications are medications, other than trial medications, which are taken by subjects any time during the on-treatment period. **Previous medications** are medications, other than trial medications and pre-medications for trial drug, which are taken and stopped before first administration of trial drug.

Prior and concomitant medications will be summarized from the “Concomitant Medications Details” eCRF page.

In cases where the date values do not allow unequivocal allocation of a medication to concomitant (as opposed to previous) medication the medication will be considered as concomitant medication.

Summary of prior and concomitant medications will include the number and percentage of subjects by Anatomical Therapeutic Chemical (ATC) Classification level 2 and preferred term based on the WHO-DD dictionary current version. A subject will be counted only once within a given drug class and within a given drug name, even if he/she received the same medication at different times. If any prior or concomitant medication is classified into multiple ATC classes, the medication will be summarized separately under each of these ATC classes. The summary tables will be sorted on decreasing frequency of drug class and decreasing frequency of drug name in a given drug class. In case of equal frequency regarding drug class (respectively drug name), alphabetical order will be used.

A listing of concomitant medications will be created with the relevant information collected on the “Concomitant Medications Details” eCRF page. All concurrent procedures, which were undertaken any time during the on-treatment period, will be summarized according to the CRF page “Concomitant Procedures Details”.

Number of subjects with concurrent procedures will be tabulated overall and by type of procedure (as classified by medical review)

A listing of concurrent procedures will be created with the relevant information collected on the “Concomitant Procedures Details” eCRF page.

In addition, a listing of premedication will be created with the relevant information collected on the “Premediation Details” eCRF page.

14.2 Subsequent Anti-Cancer Therapies/Procedures

Anti-cancer treatment after discontinuation will be provided in a data listing with data retrieved from “Anti-Cancer Treatment after Discontinuation Details”, “Radiotherapy after Discontinuation”, and “Surgery after Discontinuation” eCRF pages. The earliest date of start of new anti-cancer drug therapy will be used for the definition of the on-treatment period.

15 Treatment Compliance and Exposure

Analysis sets: ITT analysis set / Safety analysis set

All dosing calculations and summaries will be based on “avelumab Administration Details” CRFs pages.

Subjects will receive an IV infusion of avelumab at a dose of 10 mg/kg (over the duration of 1 hour) once every 2 weeks (one cycle). Analysis of exposure will be based on the calculated actual dose levels (total dose administered/weight, mg/kg). The last available weight of the subject on or prior to the day of dosing will be used.

In case of missing total dose, the dose level as entered in the eCRF will be used.

The duration of therapy (in weeks) during the study is defined as:

$$\text{duration} = \left(\frac{\text{date of last dose} - \text{date of first dose} + 14}{7} \right)$$

The cumulative dose (mg/kg) per subject in a time period is the sum of the actual dose levels that the subject received within that period (i.e. total dose administered (mg) / weight (kg)).

Each cycle is defined by a 2-week period. The dose intensity and the relative dose intensity will be calculated for each subject across all cycles. The dose intensity (mg/kg/cycle) per cycle is defined as

$$\text{dose intensity} = \left(\frac{\text{Cumulative dose}}{(\text{duration of therapy (in weeks)})/2} \right)$$

The relative dose intensity is defined as the actual dose intensity divided by the planned dose per cycle.

The summary of treatment exposure and compliance table will include the following information:

- Duration of therapy (weeks)
- Total number of infusions received
- Cumulative dose of therapy (mg/kg)
- Dose intensity (mg/kg/cycle)
- Relative dose intensity of therapy (%)

A listing of treatment exposure and compliance will also be created to summarize the information listed above for each subject.

Dose Reduction

A dose reduction is defined as actual non-zero dose < 90% of the planned dose. Number of subjects with at least one dose reduction as well as a breakdown of dose reductions (1 / 2 / 3 / ≥ 4) will be summarized.

Dose Delays

Delays will be derived based on infusion date and will be grouped into the following categories based on the deviation of the actual to the planned treatment administration day (relative to the previous treatment administration date):

- No delay (including 1-2 days delays)
- 3-6 days delay
- 7 or more days delay

For example, if one subject receives the study drug on day 1, then the next study drug administration date will be on day 15; however, if the subject receives the study drug at day 16 or 17, this is considered as 'no delay'.

The categorization is based on the maximum length of delay, i.e. the worst case of delay if subjects have multiple dose delays will be summarized.

A listing of study drug administration will be created with the information collected on the "Avelumab Administration Details" eCRF page.

16 Endpoint Evaluation

The subsections in this section include specifications for analyzing clinical trial endpoints specified in the Clinical Trial Protocol to meet the trial objectives, as well as any endpoints not identified in the Clinical Trial Protocol.

16.1 Primary Endpoint Analyses

Analysis sets: ITT analysis set, PP analysis set

The primary endpoint is the confirmed BOR to therapy in terms of either CR or PR according to RECIST 1.1 (Appendix I), as determined by an IERC. The tumor response will be based on the IERC assessment of overall response at each time point. In case of different dates of scans within the same tumor assessment visit, the earliest scan date should be used as the date of tumor assessment.

The confirmed BOR is defined as the best response obtained among all tumor assessment visits after start of trial treatment until documented disease progression, excluding assessments after start of subsequent anticancer therapy, taking requirements for confirmation into account as detailed below. The confirmed ORR will be defined as the proportion of subjects with a confirmed BOR of PR or CR.

A separate Imaging Data Management Plan and Data Transfer Plan will be created to summarize the details of the data structure and data delivery schedule of IERC assessment results.

The following requirement is taken into account for confirmation of response:

- PR or CR needs to be confirmed at a subsequent tumor assessment, preferably 6 weeks after the initial observation of response and according to the normal 6-week assessment schedule but no sooner than 5 weeks after the initial documentation of CR or PR.
- PR can be confirmed at an assessment later than the next assessment after the initial documentation of PR.
- The minimum duration for a BOR of SD is defined as at least 6 weeks after start of study treatment.

Table 2 summarizes the derivation rules described by [Eisenhauer, et al.](#) for the BOR when conformation from subsequent assessment is needed (5).

Table 2 Best overall response when confirmation of CR/PR is required

| Overall response 1st time point | Overall response subsequent time point | Best overall response (BOR) |
|---------------------------------|--|-----------------------------|
| CR | CR | CR |
| CR | PR | SD, PD or PR ^a |

| Overall response 1st time point | Overall response subsequent time point | Best overall response (BOR) |
|--|---|---|
| CR | SD | SD provided minimum criteria for SD duration met; otherwise, PD |
| CR | PD | SD provided minimum criteria for SD duration met; otherwise, PD |
| CR | NE | SD provided minimum criteria for SD duration met, otherwise NE |
| PR | CR | PR |
| PR | PR | PR |
| PR | SD | SD |
| PR | PD | SD provided minimum criteria for SD duration met, otherwise, PD |
| PR | NE | SD provided minimum criteria for SD duration met, otherwise NE |
| NE | NE | NE |

CR = complete response, PR = partial response, SD = stable disease, PD = progressive disease, NE = in-evaluable.

^a If a CR is truly met at first time point, then any disease seen at a subsequent time point, even disease meeting PR criteria relative to baseline, makes the disease PD at that point (since disease must have reappeared after CR). Best response would depend on whether minimum duration for SD was met. However, sometimes 'CR' may be claimed when subsequent scans suggest small lesions were likely still present and in fact the subject had PR, not CR at the first time point. Under these circumstances, the original CR should be changed to PR and the best response is PR.

The analysis of the primary endpoint will be conducted for the ITT analysis set. The test statistic of the exact binomial test will be calculated and compared with the thresholds given in Section 7 to determine whether the null hypothesis of an $ORR \leq 20\%$ can be rejected at the interim analysis, or, if not rejected at the interim, at the primary analysis. The thresholds given in Section 7 were chosen based on the binomial distribution:

- The binomial probability of 20 or more responses in 56 subjects under a true response rate of 20% is 0.0045.
- In case of an ITT population of 88 patients, the binomial probability of 26 or more responses in 88 subjects under a true response rate of 20% is 0.0211.
- In the case of 88 patients, the probability of rejecting the null hypothesis in the interim or the primary analysis, given a true response rate of 20%, is 0.0211, obtained via the exact calculation described in Jennison and Turnbull(1), Section 12.1.2, Formula 12.5-12.7. The associated confidence interval would not include 20%. If the ITT population would not be 88 patients, the calculation of the rejection boundaries would still be by Jennison and Turnbull (1).

Therefore, the overall Type I error rate is controlled at a level of 2.5% (one-sided).

As some subjects included in the interim analysis will be followed up until the time of the primary analysis, some subjects' BOR might change from non-response at the interim analysis to response at the primary analysis. As the parameter of interest is the response at the time of the primary analysis, the actual type I error rate of this study might be slightly smaller than designed.

The Clopper-Pearson method will be used to calculate the two-sided CI for the ORR at both the interim and the primary analysis (exact confidence interval for a binomial proportion as computed by default by the FREQ procedure using the EXACT option). In order to account for the two-stage group sequential design as applied in this study, the repeated CI method according to Jennison and Turnbull (1), Section 12.1.4, will be used to construct the two-sided CI for the interim and the primary analysis. For the interim analysis, the nominal p-value threshold of the exact binomial test of 0.0045 will be applied to calculate the two-sided CI; for the primary analysis, a p-value threshold of 0.0205, obtained as the difference between the overall type I error rate of 0.025 and the interim p-value threshold of 0.0045, will be applied to calculate the two-sided CI. This approach results in a two-sided 99.1% CI and 95.9% CI at the interim and the primary analysis, respectively.

The repeated CIs constructed in this way are simultaneous CIs for the ORR, i.e. the probability that both CIs contain the true response rate Θ is at least 95% for all possible values of Θ . They are slightly conservative in relation to the exact group sequential test procedure: In the case of exactly 25 responses in 84 subjects, the null hypothesis will be rejected, however the respective 95.9% CI for the ORR is given by (0.199, 0.412) and does not exclude the value of 0.2. The nominal p-value from the exact binomial test will also be reported.

In addition, the unadjusted 95% CIs of the ORR will also be calculated with the Clopper-Pearson method at the interim and the primary analysis in order to provide comparable results based on the PP analysis and subgroup analysis.

In addition, the number and percentage of subjects with BOR of CR, PR, SD, PD, non-CR/non-PD, and NE will be tabulated. Patients with BOR of NE will be summarized by reason for having NE status. The following reasons will be used:

- No post-baseline assessments
- All post-baseline assessments have overall response NE
- New anticancer therapy started before first post-baseline assessment
- SD of insufficient duration (tumor assessment <6 weeks after start date without further evaluable tumor assessment)

The primary endpoint analysis will be repeated for the PP analysis set as a sensitivity analysis if the PP analysis set includes less than 95% of subjects in the ITT analysis set. The ORR will be calculated along with the two-sided 95% Clopper-Pearson CIs.

According to Section 5.3.1 Inclusion Criteria of the clinical protocol, all subjects who are enrolled to the study to receive at least one dose of avelumab should have measurable disease at baseline by RECIST 1.1 according to investigator assessments. However, it is possible that a subject in the ITT analysis set could be found to have no measurable disease at baseline per IERC assessment, and would not have a response in the primary endpoint analysis. Therefore the primary endpoint analysis will be repeated on subjects with measurable disease at baseline per RECIST 1.1 by the IERC as a sensitivity analysis. The ORR will be calculated along with the two-sided 95% Clopper-Pearson CIs.

The response at each scheduled tumor assessment and the BOR will be listed for each subject.

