8.5.2 Analysis of Primary Endpoint

Part A

The primary endpoint for Part A is the BOR according to RECIST 1.1, as determined by an IERC. For a BOR of PR or CR, confirmation of the response according to RECIST 1.1 (Eisenhauer 2009) will be required, preferably at the regularly scheduled 6-week assessment interval, but no sooner than 5 weeks after the initial documentation of CR or PR. Confirmation of PR can be confirmed

at an assessment later than the next assessment after the initial documentation of PR. A BOR of SD requires that a timepoint overall response of SD has been determined at a timepoint at least 6 weeks after start of study treatment. The response at each scheduled tumor assessment and the BOR will be listed for each subject. The number and proportion of BOR (defined as CR + PR) will be tabulated. The ORR will be determined as the proportion of subjects with a confirmed BOR of PR or CR.

The test statistic of the exact binomial test will be calculated and compared with the thresholds given in Section 8.1 to determine whether the null hypothesis of an $ORR \leq 20\%$ can be rejected at the interim analysis, or, if not rejected at the interim, at the primary analysis. The 2-sided 99.1% CI and the 95.9% CI will be constructed using the Clopper-Pearson method for ORR to form repeated CIs according to Jennison and Turnbull (Jennison 2000) at the interim analysis and primary analysis, respectively. The nominal p-value from the exact binomial test will also be reported.

Part B:

For Part B, the primary endpoint is durable response, defined as objective response (CR or PR) according to RECIST 1.1, determined by an IERC, with a duration of at least 6 months. Duration of response will be calculated as specified in Section 8.3.2. Subjects for whom the duration of response is censored will be treated as failures (successes) in the analysis of durable response if the censored duration of response is below (at least) 6 months, respectively. The number and proportion of subjects with a durable response will be tabulated. The DRR will be determined as the proportion of subjects with a durable response. The 95% CI for the DRR will be calculated using the Clopper-Pearson method. There will be 1 interim analysis at 3 months after the accrual of the 25th subject, with additional interim analyses possible. All interim analyses in Part B will be exploratory.

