| Planned treatment duration per subject | 
Subjects will receive avelumab treatment until significant clinical deterioration, unacceptable toxicity, or any criterion for withdrawal from the trial or trial drug is fulfilled.
 
Subjects who have experienced a confirmed complete response (CR) should be treated for a maximum of 12 months and a minimum of 6 months after confirmation, at the discretion of the investigator. If the investigator believes that a subject may benefit from treatment beyond 12 months, it may be permissible after discussion with the sponsor. In case a subject with a confirmed CR relapses after stopping treatment, but prior to the end of the
 |

| | |
|-----------------------------------|--|
| | trial, 1 re-initiation of treatment is allowed at the discretion of the Investigator and agreement of the Medical Monitor. In order to be eligible for retreatment, the subject must not have experienced any toxicity that led to treatment discontinuation of the initial avelumab therapy. Subjects who re-initiate treatment will stay on study and will be treated and monitored according to the protocol and the “until progression” schedule in the Schedule of Assessments. |
| Randomization and Blinding | Not applicable. |

7 Sample Size/Randomization

The primary endpoint of the trial is the confirmed best overall response (BOR) according to RECIST 1.1, based on independent review of tumor assessments. The objective response rate (ORR) will be determined as the proportion of subjects with a confirmed BOR of PR or CR. The trial aims at demonstrating an ORR greater than 20% by means of an exact binomial test.

The planned total sample size is 84 subjects. There will be 1 interim analysis for futility after 20 subjects have been enrolled and observed for at least 3 months and 1 interim analysis for efficacy 6 months after 56 subjects have been enrolled. The primary analysis will be conducted 6 months after the accrual of the last subject. An exploratory analysis of secondary and exploratory endpoints will be conducted 12 months after the accrual of the last subject.

The following assumptions are made for the sample size calculation:

- ORR of 35%
- overall alpha = 0.025 (1-sided) for the test of the null hypothesis of an ORR \leq 20%

The following analyses are planned:

- Futility: Enrollment will be stopped for futility if no response (confirmed or unconfirmed) is observed in the first 20 subjects after 3 months of follow-up.

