- Efficacy: A two-stage group sequential testing approach will be applied for efficacy. The null hypothesis can be rejected if 20 subjects in the interim analysis after 56 subjects, or 25 subjects in the primary analysis after 84 subjects, show a confirmed PR or CR according to RECIST 1.1. The corresponding nominal p-values of the exact binomial test are 0.0045 and 0.0214, respectively. The resulting overall probability of reaching a positive result in the interim or primary analysis under the null hypothesis assumption of an ORR \leq 20% is \leq 0.0225, as derived from the binomial distribution according to Jennison and Turnbull (1); therefore the overall type I error rate is controlled at a level of 2.5% (one-sided).

Under the given assumptions, the power to reject the null hypothesis at the interim or the primary analysis is approximately 87%.

The actual enrolment of the trial was 88 subjects, and all 88 subjects received at least one dose of study drug. With the same two-stage group sequential testing approach, the null hypothesis can be rejected if 20 subjects in the interim analysis after 56 subjects, or 26 subjects in the primary analysis after 88 subjects, show a confirmed PR or CR according to RECIST 1.1. The corresponding nominal p-values of the exact binomial test are 0.0045 and 0.0211, respectively. The resulting overall probability of reaching a positive result in the interim or primary analysis under the null hypothesis assumption of an $ORR \leq 20\%$ is ≤ 0.0223 .

Justification of the assumption of a response rate of 35% to define the trial sample size

Data presented at the International Association for Study of Lung Cancer annual meeting in 2013 suggest the blocking of PD-L1 through the administration of anti-PD-L1 monoclonal antibody has antitumor activity in tumors whose micro-environment express PD-L1. Indeed, a response rate of 83% was reported (5/6) in patients where more than 10% of the immune-infiltrating cells were PD-L1 positive. In addition, the expression of PD-L1 at the surface of the tumor has also been correlated with clinical activity of anti-PD-L1. Robust expression of PD-L1 in the immune-infiltrating cells of MCC has been reported in the literature (1) and confirmed by the Sponsor.

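### Part A SAP Section 16.1 reports the single-look tail probability (0.0211) as the two-look type I error for 88 subjects; the exact value is 0.0223, and the confidence-interval sentence that follows does not say which interval it means.

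*SAP*

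**What the plan says.** All SAP references are to the Part A SAP. Section 7 sets "overall alpha = 0.025 (1-sided) for the test of the null hypothesis" of an ORR of at most 20%. With the actual enrolment of 88, rejection requires 20 responders among the first 56 subjects or 26 among all 88, with nominal p-values of 0.0045 and 0.0211. Section 7 then gives the overall figure ("The resulting overall probability of reaching a positive result in the interim or primary analysis under the null hypothesis assumption") as at most 0.0223.

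Section 16.1 makes the exact test the decision rule: "The test statistic of the exact binomial test will be calculated and compared with the thresholds given in Section 7". Its second bullet gives 0.0211 as the single-look probability of 26 or more responses in 88. Its third bullet says that "the probability of rejecting the null hypothesis in the interim or the primary analysis, given a true response rate of 20%, is 0.0211", and attributes this to the exact group sequential calculation of Jennison and Turnbull. It continues: "The associated confidence interval would not include 20" per cent.

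Further on, Section 16.1 plans two kinds of interval at the primary analysis. One is a 95.9% repeated interval; Protocol Section 8.5.2 agrees ("The 2-sided 99.1% CI and the 95.9% CI will be constructed using the Clopper-Pearson method for ORR"). For the other, "the unadjusted 95% CIs of the ORR will also be calculated with the Clopper-Pearson method". The section acknowledges that the repeated interval can include 20% when the test rejects, but illustrates this only at the originally planned size: "In the case of exactly 25 responses in 84 subjects, the null hypothesis will be rejected", with a 95.9% interval of (0.199, 0.412).

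**The concern.** Two different probabilities carry the same value in adjacent bullets. The two-look probability can equal the final-look tail only if no path crosses at the interim and then ends below 26. Such paths exist, and they count as rejections: the null hypothesis is tested at the final look only if it was not rejected at the interim, and Section 8.2 has enrolment continue after interim success.

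The figure is the overall type I error of the only confirmatory test in the Part A SAP. Section 5 says the analyses in this SAP go into the clinical study report and regulatory submissions. A reader who recomputes the error will match Section 7 and not Section 16.1, and the figure in Section 16.1 is the more favourable of the two. A reader with a result at the boundary could also find the 95.9% interval at odds with the sentence saying that 20% is excluded.

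**Working it through.** **Inputs.** Null rate p = 0.20 and assumed rate 0.35 (SAP Section 7); interim boundary 20 of 56; final boundary 26 of 88 (25 of 84 as first planned); repeated-interval levels 99.1% and 95.9% (SAP Section 16.1, Protocol Section 8.5.2).

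**Formula.** With X₁ ~ Bin(56, p) and X₂ ~ Bin(N − 56, p) independent, and final boundary r:

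P(reject) = P(X₁ ≥ 20) + Σ (x = 0 to 19) P(X₁ = x) · P(X₂ ≥ r − x)

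**Reproducing the plan's own figures first.**

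| Quantity | Stated | Computed |
|---|---|---|
| P(≥ 20 of 56), p = 0.20 | 0.0045 | 0.004527 |
| P(≥ 25 of 84), p = 0.20 | 0.0214 | 0.021402 |
| P(≥ 26 of 88), p = 0.20 | 0.0211 | 0.021098 |
| Two looks, N = 84, p = 0.20 | ≤ 0.0225 | 0.022458 |
| Power, N = 84, p = 0.35 | about 87% | 87.2% |

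The 84-subject results confirm that the formula is the one the plan used.

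**Two looks, N = 88.**

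- Reject at the interim: 0.004527.
- Not at the interim, but at least 26 of 88 at the end: 0.017816.
- Sum: 0.02234, against 0.0211 in the third bullet of Section 16.1.
- Gap: 0.022344 − 0.021098 = 0.00125 to five decimals. This is the probability of reaching 20 of 56 and then finishing below 26 of 88.

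Treating the futility rule (no response in the first 20) as binding changes nothing at four decimals: 0.02234. An interim boundary of 21 of 56 would give 0.0214. One of 22 of 56 would give 0.02115, close to the stated value, but the plan does not use it. With the stated boundary of 20 of 56, only the final look taken alone gives 0.0211.

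**Intervals (Clopper-Pearson).**

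| Result | Level | Interval | Includes 20%? |
|---|---|---|---|
| 26 of 88 | 95.9% | (0.1995, 0.4067) | yes |
| 26 of 88 | 95% | (0.2029, 0.4022) | no |
| 25 of 84 | 95.9% | (0.1993, 0.4118) | yes, as the SAP says |
| 20 of 56 | 99.1% | (0.1999, 0.5399) | yes, only just |

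The 95.9% interval leaves 0.0205 in each tail. It excludes 20% from below only when the one-sided exact p-value is at most 0.0205, and at 26 of 88 that p-value is 0.0211. At 27 of 88 the lower limit is 0.2094 and the mismatch is gone. At the interim boundary the mismatch comes only from rounding: 0.004527 exceeds 0.0045.

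**The case against.** Five points can be made for the text as it stands.

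1. *Section 7 gives an upper bound, and 0.0211 satisfies it.* This does not help. The bound covers every ORR up to 20% and is reached at 20%, the case the third bullet describes. The second and third bullets still cannot both be 0.0211. It is true that 0.02234 exceeds 0.0223 beyond the fourth decimal; that is rounding.

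2. *The unnamed interval could be one obtained by inverting the exact group sequential test.* Because 26 of 88 lies in that test's rejection region, such an interval would exclude 20%. This stands as a possible reading, so the sentence is ambiguous and not demonstrably false. But the SAP plans no such interval at the primary analysis, and the two it does plan disagree at the boundary.

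3. *Section 16.1 already calls the repeated intervals slightly conservative and shows a boundary case.* This stands in part. The 25 of 84 example is arithmetically correct and makes the general point, but it is not the boundary that applies to 88 subjects.

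4. *Section 16.1 says the actual error may be slightly below design, because interim non-responders can become responders later.* On that argument the true error lies between 0.0211 and 0.0223, since confirmed responses are not lost. It does not rescue the bullet, which attributes its figure to the exact calculation at a true rate of 20%.

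5. *Nothing operational depends on the figure.* This is correct, and it limits the finding to reporting.

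**Conclusion.** The concern holds. For boundaries of 20 of 56 and 26 of 88 at a true ORR of 20%, the exact two-look type I error is 0.0223. Section 16.1 states 0.0211, which is the final-look tail, and so understates the error by 0.00125. The correct value is still below 0.025, so the section's conclusion about type I error control remains true. The boundaries, the decision rule and the interval levels are sound.

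The interval sentence is ambiguous, and the ambiguity matters only at exactly 26 of 88, where one planned interval includes 20% and the other does not.

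The calculation assumes independent binary responses with a common rate, the same set of 56 subjects counted at both looks, and an interim crossing counted as a rejection whatever the final count. All three match the plan's own calculation.

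**What to change.** In SAP Section 16.1 (Part A):

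- In the third bullet, replace 0.0211 with 0.0223, to agree with Section 7. Keep 0.0211 in the second bullet as the nominal final p-value.
- Replace the interval sentence with: *At exactly 26/88 the exact test, which is the decision rule, rejects the null hypothesis, while the 95.9% repeated CI (0.1995, 0.4067) still includes 20%.* The minimum alternative is to name the interval meant.
- Move the 25 of 84 illustration to 26 of 88. This is optional once the new sentence is in place.

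Keep the 99.1% and 95.9% levels, which the protocol also specifies. The cost is one number, one sentence and, optionally, one worked example in the SAP. The protocol, boundaries and decision rule do not change. The corrected error is slightly less favourable than the one printed.
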